1 SUMMARY

Full title	Donor derived cell-free DNA and rejection of kidney allografts
Coordinating Investigator	Pr [name]
Scientific Director (if applicable)	[name]
Sponsor	Organ X Foundation
Scientific justification	
Allograft rejection is a major problem worldwide and results in the loss of thousands of transplants every year, with devastating consequences for patients in terms of mortality, morbidity and quality of life. With a prevalence of approximately 20% in the first-year after kidney transplantation, allograft rejection also represents a considerable economic burden for health care systems with the associated downstream cost related to graft failure and return to dialysis. The standard strategy to monitor rejection is based on surveillance of nonspecific functional markers such as serum creatinine level, estimated glomerular filtration rate, proteinuria and circulating donor-specific anti-HLA antibodies (DSA), which lack sensitivity and specificity. The current gold standard for diagnosing allograft rejection is the biopsy which is a potentially harmful, costly and often unnecessary procedure.
 
Recently, one promising non-invasive biomarkers has emerged in various fields such as oncology or gynecology for the monitoring of the patients: the cell-free DNA. In transplantation, donor-derived cell-free DNA (dd-cfDNA) detected in the blood of transplant recipients has been proposed as a noninvasive biomarker for the detection of rejection. However, dd-cfDNA has not been assessed in an unselected and deeply phenotyped population, with the comparison to the conventional parameters including functional, clinical or immunological factors to monitor patients and detect rejection.

Main objective and primary endpoint	
Main objectives
 
To assess the association of dd-cfDNA with the presence, activity and severity of allograft rejection, and determine whether dd-cfDNA adds value to standard of care monitoring parameters in detecting kidney allograft rejection

	
Primary endpoint Kidney allograft rejection (all causes) Time Frame: Up to 10 years after kidney transplantation

Design of the study	
Type of study: Multicenter international study Time Perspective: prospective

Population of study participants	
Derivation cohort: Prospective cohort of kidney transplant recipients recruited in 2 French centers
 
Validation cohort: kidney transplant recipients in 11 North-American centers and 1 Belgian center with clinical, biological, histological and immunological data, and dd-cfDNA assessment.

Inclusion criteria	
 Recipients transplanted from a deceased or living donor, who undergone a kidney allograft biopsy with clinical, biological, histological and immunological data. Written informed consent at the time of transplantation for the center database.
Exclusion criteria	
 Combined organ transplantation Pregnant women Bone marrow transplant
Interventions or product under investigation	
This study involves minimal risk and constraints. The intervention consists in the evaluation of the risk of allograft rejection based on parameters measured as part of the standard of care and dd-cfDNA. No medicinal product is under investigation in this protocol.

Other interventions added by the study	
Gene expression measurement in allograft biopsies

Expected benefits for the participants and for society	
There will be no immediate individual benefit for the patient to participate in the study.
 
This study will be the first that evaluates the independent association of dd-cfDNA with rejection and its added value in addition to conventional features to predict kidney allograft rejection.
 
This first integrative system will improve the patient monitoring and will help physicians in decision-making process.

Minimal risks and constraints added by the study	
The intervention added by the study represents minimal risk and constraints for the patient as it will be embedded within the standard of care.
 
No additional puncture is performed; only one additional blood tube is taken for the measurement of dd-cfDNA.

Scope of the study	Kidney transplantation; non-invasive diagnosis of rejection for improving patient monitoring
Anticipated number of participants	
Number of participants with post-transplant risk evaluation:
 
Derivation prospective cohort: 1000 patients
 
External validation cohort: 1500 patients

Number of sites	
Multicenter international study involving 14 sites.
 
Derivation cohort:
 
 • Saint-Louis Hospital, Paris, France • Necker Hospital, Paris, France 
Validation cohort:
 
 • Leuven Hospital, Leuven, Belgium • Cedars-Sinai, Los Angeles, USA • UCLA, Los Angeles, USA • Emory University, Atlanta, USA • Intermountain Medical Center Transplant Services, Murray, USA • Weill-Cornell Medical School, New York, USA • New York Hospital Medical Center, New York, USA • Virginia Commonwealth University, Richmond, USA • Washington University School of Medicine in St. Louis, St. Louis, pediatric department • Washington University School of Medicine in St. Louis, St. Louis, adult department • Transplant Institute, Tampa General Hospital, Tampa, USA • University of Wisconsin, Madison, USA
Schedule for the study	
Inclusion period 2011- 2022;
 
Participation period (follow-up): Derivation and validation cohorts: up to August 2022

Expected number of enrolments per site
	
Derivation cohort (n=1000)
 
External validation cohorts (n=1500)


Statistical analysis
	
Continuous variables will be described using means and standard deviations (SDs) or median and the interquartile range. We will compare means and proportions between groups using Student's t-test, analysis of variance (ANOVA) (Mann-Whitney test for donor specific antibodies (DSA) mean fluorescent intensity) or the chi-square test (or Fisher's exact test if appropriate).
 
We will evaluate the association between the dd-cfDNA levels and each allograft diagnosis (ABMR, TCMR, Mixed rejection, glomerulitis without rejection, polyomavirus nephritis, fibrosis, borderline changes, no specific lesions). Then, to investigate the association of dd-cfDNA with rejection severity, we will compare the mean dd-cfDNA level according to each active and chronic Banff lesion score (ranked from 0 to 3).
 
Evaluation of the association between dd-cfDNA and rejection
 
The associations between allograft rejection and clinical, functional, and immunologic factors will be first computed using logistic regression analyses. The factors identified in these analyses will be thereafter included in a final multivariable analysis if the p-value of the Wald test is < 0.1. Multivariable logistic regression analysis will be performed using a stepwise backward elimination until each predictor is associated with allograft rejection with a p-value below 0.05. The internal validity of the final model will be confirmed using a bootstrap procedure, which involves generating 1,000 datasets derived from resampling the original dataset and permitting the estimation of the biased corrected 95% CI and the accelerated bootstrap OR.
 
Assessment of the added value of dd-cfDNA
 
To evaluate the added value of dd-cfDNA, we will assess the performances of the reference model (including independent standard of care predictors of the final multivariable model) with and without dd-cfDNA to evaluate to risk of rejection. The performances of the models to predict rejection will be evaluated with the use of the accuracy of the model, which will be assessed based on its discrimination ability and calibration performance. For each model, the discrimination ability (i.e., the ability to separate patients with different prognoses) of the final model will be evaluated using Area under the curve (AUC). Calibration (the ability to provide unbiased rejection predictions in groups of similar patients) will be assessed based on a visual examination of the calibration plots.


	
We will follow the TRIPOD (Transparent Reporting of a Multivariable Prediction Model for Individual Prognosis or Diagnosis) statement for reporting multivariable prediction model development and validation.
 
Sensitivity analyses: We will investigate the independent association of dd-cfDNA with rejection and its added value in predicting rejection in different clinical scenarios (biopsies performed during the first year or after one-year post-transplantation, according to the subtypes of rejection, protocol biopsies or biopsies performed for clinical indication) and according to the patient ethnicity.
 
We will use R (version 4.1.2, R Foundation for Statistical Computing) and STATA (v17) for the descriptive and prediction analyses. Values of $p < 0.05$ will be considered significant, and all tests will be 2-tailed.

Sources of monetary support	The study is funded by the OrganX Foundation

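### Does leaving the unit of analysis unstated (patient or biopsy) undermine the logistic regression, the variable selection and the bootstrap?

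*Combined protocol and SAP*

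**What the plan says.** All the relevant text is in Section 1 Summary.

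- **Main objective and primary endpoint.** The objective concerns "the presence, activity and severity of allograft rejection". The endpoint is "Kidney allograft rejection (all causes) Time Frame: Up to 10 years after kidney transplantation". Neither says which biopsy counts.
- **Inclusion criteria.** Recipients are eligible "who undergone a kidney allograft biopsy", in the singular, with no statement on repeat biopsies.
- **Minimal risks and constraints.** "only one additional blood tube is taken for the measurement of dd-cfDNA".
- **Anticipated number of participants.** Sizes are counted in patients: "Derivation prospective cohort: 1000 patients", and 1500 patients for external validation.
- **Scope of the study.** The purpose is "non-invasive diagnosis of rejection for improving patient monitoring".
- **Statistical analysis.** For severity, "we will compare the mean dd-cfDNA level according to each active and chronic Banff lesion score". Associations with rejection "will be first computed using logistic regression analyses". A Wald screen at p < 0.1, backward elimination at p < 0.05 and a bootstrap of 1,000 resampled datasets follow. No resampling unit, clustered variance, GEE or random effect is named. Discrimination and calibration are both explained in terms of patients.
- **Sensitivity analyses.** Biopsies are split by time since transplantation (first year or later) and by protocol versus clinical indication.

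**The concern.** Two strands of wording seem to pull apart. The cohort sizes and the performance measures refer to patients, while the Banff comparisons and the sensitivity analyses refer to biopsies. Inclusion runs from 2011 to 2022, the endpoint window is 10 years, and both protocol and indication biopsies are eligible. A patient could therefore have been biopsied more than once, and no rule limits a patient to one row.

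If repeat biopsies entered as separate rows, naive standard errors would generally be too small for predictors positively correlated within patient. More noise variables would pass the 0.1 screen and the 0.05 retention step, and those steps build the reference model against which the added value of dd-cfDNA is judged. A bootstrap that resampled rows would repeat the error and not reveal it. The t-test, ANOVA, Mann-Whitney and chi-square comparisons also assume independent rows.

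**Working it through.** **No planned figure to reproduce.** The document has no power calculation and gives neither biopsies per patient nor within-patient correlation. The check is a reading of the text, followed by a conditional calculation.

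**Step 1: what the text supports.** Inclusion criterion, blood tube, cohort sizes and performance wording all point to one row per patient. The wording that seems to point the other way is compatible with this. A dataset with one biopsy per patient can be tabulated by Banff score, divided at one year after transplantation, and divided by protocol versus indication. The 10-year frame can simply be the range of biopsy dates. No sentence mentions repeat biopsies.

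**Step 2: size of the effect if repeats existed.** With m biopsies in a patient, let k = Σm²/Σm − 1.

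- One each: k = 0.
- Half with one, half with two: k = (1 + 4)/(1 + 2) − 1 = 0.667.
- All with two: k = 1.

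The design effect is DE = 1 + k × ρx × ρy, where ρx and ρy are the within-patient correlations of predictor and outcome (ρx = 1 for a constant predictor). The naive SE is understated by 1 − 1/√DE. The true level of a nominal two-sided test is 2[1 − Φ(z/√DE)], with z = 1.960 (5%) or 1.645 (10%). The correlations of 0.2 and 0.6 are assumptions.

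| Setting | DE | SE understated | 5% test | 10% screen |
|---|---|---|---|---|
| One biopsy per patient | 1.000 | 0% | 5.0% | 10.0% |
| Varying predictor, half with two, ρx = ρy = 0.2 | 1 + 0.667 × 0.04 = 1.027 | 1.3% | 5.3% | 10.4% |
| Varying predictor, all with two, ρx = ρy = 0.6 | 1 + 0.36 = 1.360 | 14.3% | 9.3% | 15.8% |
| Constant predictor, half with two, ρy = 0.2 | 1 + 0.667 × 0.2 = 1.133 | 6.1% | 6.6% | 12.2% |
| Constant predictor, all with two, ρy = 0.6 | 1 + 0.6 = 1.600 | 20.9% | 12.1% | 19.3% |

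Simulation of the last four rows in the same order (6,000 runs, 1,000 patients, 20% rejection, null predictor) gave naive 5% tests at 5.5%, 10.0%, 6.8% and 12.0%. Patient-clustered tests gave 5.2%, 5.1%, 5.4% and 5.1%.

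**Step 3: how firm these numbers are.** Not firm at either end. With correlation 0.1 and half of patients biopsied twice, a constant predictor has DE = 1 + 0.667 × 0.1 = 1.067, an SE understated by 3% and a 5% test at 5.8%. With three biopsies each and correlation 0.5, DE = 1 + 2 × 0.5 = 2.0 and the 5% test is at 16.6%. With negative within-patient correlation the direction reverses: ρx = −0.2, ρy = 0.6, all with two, gives DE = 1 − 0.12 = 0.88 and a 5% test at 3.7%. The low to middle part of the table is the more relevant for dd-cfDNA and for the monitoring markers named in the scientific justification (creatinine, eGFR, proteinuria, DSA), since all of these can change between biopsies.

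**Step 4: the bootstrap.** In simulation (400 datasets, 300 resamples each), row-level intervals for a constant predictor were 0.947 (mild setting) and 0.785 (strong setting) times as wide as patient-level ones. For the varying predictor in the strong setting the ratio was 0.856. These were percentile intervals, whereas the plan specifies bias-corrected accelerated ones. Row-level coverage was 91.0% in the mild constant-predictor setting and 90.3% in the strong one, where the design effects imply about 93.4% and 87.9%. With a Monte Carlo SE of up to about 1.5 points, coverage does not separate the two settings, so this is weak support.

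**The case for a change.** The strongest reply is that a probable intention is not a rule. The statistical text gives the model, the thresholds and the number of bootstrap datasets in detail, so its silence on the unit is noticeable. Even with one biopsy per patient, nothing says which one is the index biopsy. Taking the first, the last or the one showing rejection would give different case mixes, and the choice could be made after results are known. Stating the unit would cost a sentence.

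Most of this is true. The unit, the index-biopsy rule and the resampling unit are all absent, and the conditional arithmetic is right. What it does not supply is evidence that the planned analysis is wrong. The statistical harm needs repeat biopsies per patient, which no sentence describes and several sentences lean against. The remaining point, selection of the index biopsy, is missing detail in a summary-level plan. It is not a conflict between the stated design and the stated methods. Recasting the primary endpoint as diagnosis on a paired biopsy would go further than the gap requires, because the text also speaks of risk, prediction and prognosis. That choice belongs to the sponsor.

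**Conclusion.** The concern does not call for a change. The document leaves the unit of analysis unwritten, but its wording leans to one biopsy per patient. On that reading the logistic regression, the selection thresholds and the bootstrap are valid on this point and the effect is zero.

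If the data did hold several biopsies per patient, the understatement under the assumed inputs would be about 1% to 14% on the dd-cfDNA standard error, and 6% to 21% for predictors constant within patient. Odds ratios and AUC would keep their meaning if the question is diagnosis on the biopsy; the damage would be to intervals, p-values and variable selection. Analysts would see repeated patient identifiers in the dataset and could apply patient-clustered variance and patient-level resampling, which are standard tools. Clustered variance restored near-nominal test levels in the simulations.

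The conclusion rests on reading the patient-level wording at face value. It would need revisiting only if the dataset proved to contain repeat biopsies analysed as independent rows.

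### The general tests named for means (Student's t-test and ordinary ANOVA) assume a common variance; if dd-cfDNA groups differ in both size and spread, their p-values are wrong in a direction the plan cannot know

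*Combined protocol and SAP*

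**What the plan says.** All of the relevant text is in the Combined protocol and SAP, section 1 Summary, mostly in the Statistical analysis row.

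- General rule for group comparisons: "We will compare means and proportions between groups using Student's t-test, analysis of variance (ANOVA". The one stated departure for continuous data is a "Mann-Whitney test for donor specific antibodies (DSA) mean fluorescent intensity". It covers DSA intensity, not dd-cfDNA.
- Diagnosis: dd-cfDNA is to be related to eight categories ("ABMR, TCMR, Mixed rejection, glomerulitis without rejection, polyomavirus nephritis, fibrosis, borderline changes, no specific lesions"). No test is named in that sentence.
- Severity: "we will compare the mean dd-cfDNA level according to each active and chronic Banff lesion score (ranked from 0 to 3"). No test is named here either, so the general rule applies.
- Significance: "Values of $p < 0.05$ will be considered significant, and all tests will be 2-tailed".

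No unequal-variance version, variance check or transformation of dd-cfDNA is stated. The main objective includes activity and severity of rejection as well as its presence. The Banff-score comparison of means is the only severity analysis described.

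**The concern.** Student's t-test and ordinary ANOVA estimate one within-group variance and use it for every group. The largest group dominates that estimate. With equal group sizes the error largely cancels. With unequal sizes, any real difference in SD goes straight into the standard error of the contrast.

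Equal sizes are unlikely here. The plan splits patients over eight diagnoses and over four scores per lesion, and there is no reason for the high scores to be as common as the low ones. At stake is whether p < 0.05 means what it says in the severity comparisons, and in the diagnosis comparisons if the general rule is applied there too. The same goes for any confidence interval built from the pooled variance.

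**Working it through.** **Inputs from the documents.** Two-sided alpha is 0.05. The derivation cohort has 1,000 patients ("Derivation prospective cohort: 1000 patients") and the validation cohort 1,500 ("External validation cohort: 1500 patients"). The only figure bearing on a group share is a background statement: "With a prevalence of approximately 20% in the first-year after kidney transplantation". The plan has no calculation of its own to reproduce on this point.

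**Assumptions.** All group sizes and SD ratios below are assumed. Data are normal unless stated. The total is 1,000. For given group shares the large-sample result does not depend on the total, so it carries over to 1,500.

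**Two groups, 200 v 800.** Let r be the SD of the smaller group divided by that of the larger (larger SD = 1).

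- True variance of the difference: V_true = r²/200 + 1/800
- Pooled variance of the difference: V_pool = [(199r² + 799)/998] × (1/200 + 1/800)
- True size: 2 × [1 − Φ(1.96 × √(V_pool/V_true))]

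For r = 1.5: V_true = 0.01125 + 0.00125 = 0.0125. V_pool = 1.2492 × 0.00625 = 0.00781. √(V_pool/V_true) = 0.790, and 1.96 × 0.790 = 1.549, which gives 12.1%.

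| r | true SE / pooled SE | true size | coverage of a 95% interval |
|---|---|---|---|
| 0.67 | 0.79 | 1.3% | 98.7% |
| 1 | 1.00 | 5.0% | 95.0% |
| 1.25 | 1.14 | 8.6% | 91.4% |
| 1.5 | 1.26 | 12.1% | 87.9% |
| 2 | 1.46 | 17.9% | 82.1% |
| 3 | 1.69 | 24.6% | 75.4% |

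Simulation agrees for r of 1.25 and above (8.5%, 12.0%, 17.8%, 24.9%), with the Welch test at 4.8% to 5.2% on the same data.

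**Four groups (Banff 0 to 3).** With equal means, the expected between-group mean square is Σ(1 − n_j/N)σ_j²/(k − 1), and the expected within-group mean square is Σ(n_j − 1)σ_j²/(N − k). Their ratio should be 1.

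- 700/150/100/50, SDs 1/1.25/1.5/1.75: 2.188/1.310 = 1.67. Simulated size is about 20%.
- 700/150/100/50, SDs 1/1.5/2/3: 4.788/1.879 = 2.55. Simulated size is about 35%.
- 400/250/200/150, SDs 1/1.25/1.5/1.75: 2.058/1.699 = 1.21. Simulated size is about 10%.

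Welch ANOVA stays near 5% in all three. If the SDs run the other way (2/1.67/1.33/1 over 700/150/100/50), ordinary ANOVA runs at 0.7%.

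**Does Welch work on any scale?** No. With identical lognormal distributions (log-SD 1) in groups of 700/150/100/50, ordinary ANOVA on the raw scale runs at about 5% and Welch at 10.0%. With log-SDs 0.8/0.9/1.0/1.2 and equal raw means, Welch runs at 13% and ordinary ANOVA at 17%. On the log scale, with log-SDs from 0.8 to 1.2 and equal log means, Welch holds 4.7% against 13.6% for ordinary ANOVA.

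**Is a rank test the answer?** Not by itself: for 200 v 800 with SD ratios of 1.5 to 3, the Mann-Whitney test runs at 8% to 14% for a difference in location.

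**The case against.** The strongest reply is that every percentage above rests on inputs the plan does not give. This stands. A reader might infer that the planned tests will run at 12% to 36%, but the documents do not support that. Across the settings tried, the range is from about 0% (largest group the most variable) to 51% (850/80/40/30 with SDs rising threefold). At 200 v 800 and a ratio of 1.1, the size is only 6.4%.

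Nor is 200 v 800 this cohort's own split. The 20% is a background first-year prevalence, whereas the study enrols biopsied recipients, includes biopsies for clinical indication and runs up to 10 years. The rejection share here is unknown.

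Two further readings go too far. One is that plotted error bars would be wrong: the plan mentions none, and the SDs and IQRs it does plan are computed within group. The other is that the main association or added-value result is undermined. Those rest on logistic regression, bootstrap, AUC and calibration, which pool no group variances.

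It can also be said that if spread rises only because the mean rises (constant log-scale SD), equal means imply equal SDs and the overall ANOVA holds its 5%. That is correct for the overall null. It does not protect intervals or pairwise contrasts based on the pooled variance once some group means differ, and nothing in the documents shows that log-scale SDs are constant.

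What survives is narrower. The plan prespecifies a test whose validity depends on equal variances, in groups that are probably unequal in size, for the only severity analysis it describes.

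**Conclusion.** The point holds as a conditional weakness. If sizes and SDs both differ, the pooled standard errors, p-values and any intervals built from them are wrong: anti-conservative when the smaller groups are more variable, conservative when they are less so. The illustrations run from about 1% to 25% for 200 v 800 (SD ratios 0.67 to 3), and from about 10% to 35% for four groups with SDs rising with the score. All assume group sizes, SD ratios and normal data.

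A reader might conclude that a false severity finding is far more likely than 5%. The documents do not show this, because the direction depends on SDs they do not give. That the general tests also apply to the eight diagnoses is an inference from the general rule. The change should be made before analysis because it costs little. It does not call the rejection model into question.

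**What to change.** In the Statistical analysis row of the Summary, replace the general rule for means with text such as: *dd-cfDNA will be compared between diagnoses and between Banff scores on the log scale and summarised by geometric means, using the Welch t-test for two groups and Welch ANOVA for more than two, with Games-Howell for pairwise contrasts. Other continuous variables that are not strongly skewed will be compared with the Welch versions on their original scale.* Do not apply Welch to raw, strongly skewed dd-cfDNA.

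Costs:

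- A short change to the text; the methods are standard in the R and STATA the plan already names.
- The contrast becomes a ratio of geometric means instead of a difference in arithmetic means. If log-scale SDs differ, these are different null hypotheses, so the severity sentence, which speaks of the mean level, must be reworded to match.
- A rule is needed for any dd-cfDNA values recorded as zero.
- Power loss is negligible if variances are equal: 79.5% for Welch against 79.8% for Student at 200 v 800, with normal data.

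### The severity analysis compares mean dd-cfDNA across Banff scores with no stated restriction to rejection biopsies or adjustment for subtype, so for rejection-linked lesions it cannot separate severity from presence

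*Combined protocol and SAP*

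**What the plan says.** All references are to the combined protocol and SAP, section 1 Summary.

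- **Main objective.** "To assess the association of dd-cfDNA with the presence, activity and severity of allograft rejection". Presence and severity are separate items.
- **Inclusion criteria.** Recipients "who undergone a kidney allograft biopsy with clinical, biological, histological and immunological data". A finding of rejection is not required.
- **Statistical analysis, diagnoses.** dd-cfDNA is first compared across "each allograft diagnosis (ABMR, TCMR, Mixed rejection, glomerulitis without rejection, polyomavirus nephritis, fibrosis, borderline changes, no specific lesions"). On this list a lesion such as glomerulitis can be present without rejection.
- **Statistical analysis, severity.** Next, "to investigate the association of dd-cfDNA with rejection severity", the plan says "we will compare the mean dd-cfDNA level according to each active and chronic Banff lesion score (ranked from 0 to 3"). The tests named for comparing means are the t-test and ANOVA, neither adjusted.
- **Sensitivity analyses.** "We will investigate the independent association of dd-cfDNA with rejection and its added value in predicting rejection in different clinical scenarios", including "according to the subtypes of rejection, protocol biopsies or biopsies performed for clinical indication". These cover the association with rejection and the added value, not the lesion-score comparison.

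The multivariable logistic model has rejection as its outcome, so it does not analyse severity.

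**The concern.** For a lesion that is commoner in rejection, the share of biopsies with rejection rises with the score. A marker that goes up when rejection is present, and does not change further as rejection worsens, then has a higher mean at each higher score. The planned comparison would register this as a relation with severity.

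At stake is one part of the main objective. A reader could be told that dd-cfDNA rises with the severity of rejection when the data show only that it rises with rejection. The preceding comparison across diagnoses would make the presence effect visible and so help interpretation, but it does not remove that effect from the score comparison.

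**Working it through.** The plan gives no effect size, SD or error rate for this analysis, so there is no figure of its own to reproduce. The check asks what the comparison yields when there is no severity effect.

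**Inputs from the plan.** Derivation cohort 1000; two-sided 0.05; rejection about 20%. The last is a first-year prevalence in the Scientific justification, used here as the share of biopsies with rejection.

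**Assumptions, not in the plan.** One biopsy per patient; log-normal dd-cfDNA with log-SD 1.0; rejection multiplies dd-cfDNA by f = 1.5, 2 or 3. Score distributions, in % for scores 0/1/2/3:

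| Link to rejection | Without rejection | With rejection |
|---|---|---|
| Strong | 85/10/4/1 | 25/25/30/20 |
| Moderate | 85/10/4/1 | 50/25/15/10 |
| Weak | 60/25/10/5 | 50/27/14/9 |
| None | 50/25/15/10 | 50/25/15/10 |

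**Step 1: share with rejection at each score.** P(rejection | s) = 0.2·r(s) / [0.2·r(s) + 0.8·n(s)], where r and n are the score shares with and without rejection. For the strong link:

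- score 0: 0.050/(0.050 + 0.680) = 0.07
- score 1: 0.050/(0.050 + 0.080) = 0.38
- score 2: 0.060/(0.060 + 0.032) = 0.65
- score 3: 0.040/(0.040 + 0.008) = 0.83

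The moderate link gives 0.13/0.38/0.48/0.71 and the weak link 0.17/0.21/0.26/0.31. With no link the share is 0.20 throughout.

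**Step 2: mean by score for a presence-only marker.** Relative to the non-rejection mean it is 1 + (f − 1)·P(rejection | s). For f = 2 and the strong link this gives 1.07, 1.38, 1.65 and 1.83: a steady rise with no severity effect.

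**Step 3: how often the comparison is significant.** Simulation, 2,000 datasets per setting, ANOVA on untransformed values, all biopsies:

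| Link | f = 1.5 | f = 2 | f = 3 |
|---|---|---|---|
| Strong | 58% | 95% | 99.9% |
| Moderate | 30% | 63% | 92% |
| Weak | 7% | 11% | 18% |
| None | 5% | 5% | 5% |

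For strong and moderate links almost every significant result has a rising slope. Varying the rejection share from 10% to 30% gives 34-99.9%, 20-95%, 7-21% and 4-5% in the same row order. The same ANOVA within rejection biopsies gives 3.4-6.2% in every setting, provided that dd-cfDNA does not differ by subtype.

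**Step 4: if the analysis is already restricted.** Take 200 rejection biopsies, with subtypes ABMR, TCMR and mixed in shares 45/40/15. ABMR and mixed are raised 1.5- or 2-fold over TCMR, with no gradient within subtype. Assumed scores (ABMR; TCMR; mixed):

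- strong: 10/25/35/30; 70/20/7/3; 25/25/30/20
- moderate: 25/25/30/20; 50/25/15/10; 35/28/22/15
- weak: 25/25/30/20; 35/28/22/15; 30/26/26/18

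At log-SD 1.0, unadjusted ANOVA is falsely significant in 18% and 40% (strong subtype link), 6% and 10% (moderate) and about 5% (weak). With subtype in the model the rate is 3.2-6.4% across the settings examined.

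**The case against.** The strongest objection is that the population is unstated rather than wrong. The comparison is introduced as one of rejection severity, which can be read as confined to rejection biopsies, and then the all-biopsy rates do not apply. This stands in part. That all biopsies will be used is an inference from the inclusion criteria and the neighbouring list of diagnoses, not something the plan states. But nothing states the restriction either, and under restriction the subtype problem in step 4 remains.

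A reader might also infer that p < 0.05 is the plan's sole rule for declaring a severity effect. The text does not support that. It is a general significance convention; the plan also uses p < 0.1 for entry to the multivariable model and judges calibration by eye. No passage says when severity would be declared, and the comparison could be meant as descriptive. Still, severity is part of the main objective, ANOVA is named for comparing means, and a p-value is therefore likely.

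Finally, the plan does not say how rejection is diagnosed. If lesion scores help to define rejection or its subtypes, conditioning on either removes part of the severity range. This stands, and it limits how the corrected analysis may be read.

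**Conclusion.** The concern holds in a limited form. As written, the comparison cannot separate severity from presence for rejection-linked lesions, and neither the logistic models nor the sensitivity analyses by subtype repair this. The direction follows from the design if all biopsies are used. The size does not: score distributions, fold changes, log-SD and subtype shares are assumed, and the 20% is a background prevalence, not a proportion of biopsies.

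A reader might go further and conclude that a severity claim from this study would be false, or that its other results are undermined. The plan supports neither. A true gradient may exist, lesions unlinked to rejection are not affected, and the problem does not reach the rejection models or the added-value analysis. It is a change that should be made for one component of the main objective.

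**What to change.** In the Statistical analysis text, state that the severity conclusion rests on the lesion-score comparison among rejection biopsies, adjusted for rejection subtype (ABMR, TCMR, mixed), and label the all-biopsy comparison descriptive. State how rejection and its subtypes are diagnosed. If either is defined by lesion scores, both the restriction and the subtype adjustment narrow the score range, and the result should be read as a gradient among diagnosed rejections.

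No new data are needed. The cost is precision: about 0.20 × 1000 = 200 biopsies, if the 20% applied per biopsy. For an assumed gradient of 0.2 log-SD per grade at log-SD 1.0, subtype-adjusted power with 200 biopsies is about 38-49% for ANOVA on untransformed values and 70-85% for a trend test on the log scale. If diagnosis required a score of at least 1, the trend test would have about 56-61%. Subtype adjustment costs the trend test about 18 points (88% to 70%) when the lesion is strongly tied to subtype and about 3 points (87% to 84%) when moderately tied.

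A trend test, the log scale, and an all-biopsy model adjusted for diagnosis category are optional additions.
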